3.2 Any Treatment Error

During SOAP note evaluation, the MO is asked to indicate whether the treatment plan for the patient contains any error, conditional on the MO’s own diagnosis.

The introductory text (here for SOAP Note A) is:

Treatment in SOAP Note A:

Please evaluate whether the treatment in SOAP Note A is appropriate for this patient’s condition.

Please base this on *your own diagnosis*, not the CHEW’s diagnosis in SOAP Note A.

The treatment includes medications as well as other care instructions, such as information on home care or referrals.

This is followed by the question:

Is the treatment plan for the patient in SOAP Note A completely appropriate given your *own* diagnosis (accounting for conditional treatments based on medical tests)?

Answer “No” if the patient should receive different medical care given your diagnosis. This can include both minor differences (for example, the patient should be advised to rest) and major errors (for example, the patient should receive a completely different set of medications).

(Answer options: yes/no/unsure)

If the answer is yes, the MO is asked to confirm once more. The same question is asked for SOAP Note B. We will code this question as an indicator variable that equals 1 if the treatment in the SOAP note contains an error and 0 otherwise.

3.3 Severe Treatment Error

The distribution of treatment error harm ratings is expected to be heavily skewed, with a large proportion of zeros.

We define severe errors as any errors (as above) that generate a harm rating at or above the 95th percentile of harm on the unassisted scale (pooling child and adult scales).

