DALY benchmarks are derived from previously published DALY or QALY estimates from the medical research literature, and from novel calculations of expected harms, which employ prior estimates of the utility weights of various health states, of the effects of various medical interventions, and of life expectancy in Nigeria (both absolute and quality adjusted).

To create a consistent scale, specific DALY benchmarks are associated with cutoff points that are described in broad clinical terms, capturing the general nature of the harms.

MOs will first be presented with the following survey prompt:

“Consider the overall health harms from the treatment errors in SOAP Note [A/B] that you just described (temporary symptoms and risk of longterm or permanent harm).

The scale below shows levels of harm that average [adults/children] experience due to different medical errors, ordered from least to most severe.

Harm is expressed in terms of ‘healthy time lost’.

For example, unpleasant symptoms for 6 days reduce quality of life by 1/3 for those days, resulting in the equivalent of 2 days of life lost.

Please select the appropriate interval of the harm scale for SOAP Note [A/B].”

Below this prompt, the scale of different levels of harm is shown in table form, as in figure 1.

[figure not shown]

Figure 1: Initial Rank Ordering (Adult Scale)

The MO uses the multiple-choice response option in the bottom to select an interval on the scale.

On the next screen, they see a detailed description of the two scale end-points and use a slider to choose the estimated level of harm between those two points, see Figure 2 for an example.

The DALY scale has 9 benchmarks from 0 minutes to 23 years (28 years for children), generating 8 “bins” each. They are described in detail in Appendix C.

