2.5 MD Panel

A panel of three Medical Doctors (MDs) will review the patient data (CHEW notes, MO notes, and LLM feedback).

Flagging MO error. In a first step, they will review the MO notes only and record whether there is any error in the diagnosis or treatment proposed in the conditional note or in the final note. If an error is identified the MDs will rate the error by severity to distinguish medical mistakes from differences in opinion about a patient who is not present.

SOAP note rating. Next, the MDs will carry out an independent evaluation of the assisted and unassisted SOAP notes as described in the sections “Types of harm incurred” and ”“Measuring Healthy Time Lost” (section 2.3.1 above).

LLM review. Finally, the MDs will also review the LLM feedback and answer the following questions:

“Did the CHEW follow all, some, or none of the LLM recommendations?”

If some or none: "Imagine the CHEW had followed all the recommendations of the LLM. Would the resulting treatment plan be an improvement over their assisted note?" (Yes/no)

If yes: "Please explain."

“Did the LLM make any mistakes?” (Yes/no)

If yes: "Was any aspect of the CHEW's assisted treatment plan worse than the unassisted plan because the CHEW followed the LLM's erroneous recommendation?"

If yes: "Please explain."

3 Primary Outcomes

Our study will have four primary outcomes, each assessing differences between the CHEW's assisted and unassisted note.

1. An indicator for an error in the treatment plan in the SOAP note (with the potential for harm)
2. An indicator for an error in the treatment plan that causes a loss of at least X quality-adjusted life days (where X is the highest benchmark on the appropriate DALY scale so that at least 5% of patients have an error that large in the unassisted SOAP note)
3. An indicator for the better treatment plan

4. Consistency of treatment with the “standard of care” based on our screening tests and medical guidelines.

We describe the construction of each metric in detail below.

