4.6 Average and Distribution of DALY lost

We use our DALY measure of harm indirectly in several primary outcomes (probability of error and severe error, which note is the better note). As a secondary outcome, we will measure the effect of LLM assistance on average DALY (this is not our primary outcome because we are concerned about power being limited due to a few outliers).

Additionally, we will show the full distribution of DALY ratings for the assisted and unassisted notes.

4.7 3rd Party MD Review of CHEW notes and MO notes

We will reassess our primary outcomes using the MD DALY ratings and subjective harm measures (section 2.5).

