4.8 MO Review Only for Subset Approved by MDs

On the one hand, the reviewing MOs have the best information about the patient, but on the other, they may also make medical errors. Therefore we will also consider replicating our primary outcomes looking only at patients for whom MDs do not identify a serious error in the diagnosis or treatment proposed in the “final” MO note (see section 2.5). We will only drop patients for this secondary outcome if at least two MDs agree on the error identified in the MO’s note.

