5.4 Updates 4/29/2025

We have several updates to the pre-analysis plan – these updates are made prior to analyzing the data by treatment status.

On 2/25, we discovered a randomization error in the order of the notes as presented to the MO (the unassisted note was always presented first, rather than in random order). Due to this error, we are throwing out all observations from prior to 2/25 in any analyses that use MO generated outcomes. Analyses that rely on outcomes not generated by the MO (e.g. objective test data) will still use all data, including the data gathered prior to 2/25.

As a result of these changes, we are extending the timeline of the initial study. The current proposed end date is May 30th.

A Criteria for Screening Tests

We apply the following demographic and symptom screening criteria for the medical screening tests.

Malaria RDT: All demographics are eligible. Malaria testing is offered if the patient reports a fever in the last 24 hours.

Anemia/PCV: All patients 18 years and older.

The test is offered for patients reporting feeling tired or with low energy for 4 weeks or more, feeling like their heart is racing for 4 weeks or more, signs of bleeding for 4 weeks or more (vaginal bleeding, blood in stool or in urine), feeling dizzy, difficulty breathing, currently pregnant, and delivered a baby within the past six weeks.

Urine dipstick analysis: Only female patients 7 years or older.

Urine dipstick analysis is offered for patients reporting pain while urinating, blood in urine, frequent urge to urinate, abnormal discharge from the genital area, and burning feeling while urinating.

B Treatment guidelines for malaria, anemia and UTI

- For malaria, conditional on testing positive (and meeting the symptom screen), the essential treatment guidelines are:

Adults: Artemether-Lumefantrine 80 mg/480 mg by mouth twice daily for 3 days

Children 5-14 Kg: Artemether-Lumefantrine 20 mg/120 mg by mouth twice daily for 3 days

Children 15-24 Kg: Artemether-Lumefantrine 40 mg/240 mg by mouth twice daily for 3 days

Children 25-34 Kg: Artemether-Lumefantrine 60 mg/360 mg by mouth twice daily for 3 days

Severe malaria: Artemether 3.2 mg/Kg IM loading dose once followed by 1.6 mg/kg IM maintenance dose once daily for 3 days

- For anemia, conditional on testing positive (and meeting the symptom screen), the essential treatment guidelines are:

Adults: Ferrous Sulfate 200 mg by mouth once daily for one month

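### The severe-error primary outcome has two different definitions: a scale-specific benchmark in Section 3 item 2 and a pooled 95th percentile in Section 3.3

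*SAP*

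**What the plan says.** Section 3 item 2 introduces the outcome as "An indicator for an error in the treatment plan that causes a loss of at least X quality-adjusted life days", and fixes X in the same sentence: "where X is the highest benchmark on the appropriate DALY scale so that at least 5% of patients have an error that large". The 5% refers to unassisted notes. X is therefore one of the Table 1 points, read on the adult or the child scale. The list of outcomes ends with "We describe the construction of each metric in detail below".

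Section 3.3 then defines a severe error as any error with a "harm rating at or above the 95th percentile of harm on the unassisted scale (pooling child and adult scales"). It mentions no benchmark, and one cut serves both age groups.

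Two other parts of the SAP bear on whether these can coincide:

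- Section 2.3.1 has the medical officer (MO) pick an interval and then "use a slider to choose the estimated level of harm between those two points", so ratings are not confined to benchmarks.
- Table 1 in Appendix C gives adults and children different benchmarks at every non-zero level.

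The update in Section 5.4 does not say which rule governs.

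**The concern.** The two sections describe the same primary outcome but differ on two points: fixed benchmark or empirical percentile, and age-specific or pooled. Item 2 makes 5% a floor with no ceiling on the unassisted event share. Section 3.3 makes the share about 5%, apart from ties. Two analysts who each followed the SAP could report different events, different counts and a different effect estimate.

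Both cuts depend on the data, so an unresolved choice also leaves room to settle the definition after results are seen.

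The conflict carries forward. Section 4.7 says "We will reassess our primary outcomes using the MD DALY ratings", Section 4.8 considers "replicating our primary outcomes looking only at patients for whom MDs do not identify a serious error", and Section 4.9 repeats the primary outcomes without patients for whom the MO recommends triage. Each inherits the ambiguity.

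Item 2 has a gap of its own: it does not say whether the 5% of patients is counted within each scale or over all patients.

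**Working it through.** The SAP states no event count or power figure for this outcome, so there is none to reproduce. The check applies both rules to the same ratings.

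**Benchmarks (Table 1)**

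| Scale | Non-zero benchmarks |
|---|---|
| Adult | 20 min, 150 min, 24 h, 8 d, 9 wk, 26 wk, 6 y, 23 y |
| Child | 45 min, 300 min, 12 h, 28 d, 11 wk, 22 mo, 7.5 y, 28 y |

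No non-zero value is shared.

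**Logic.** On one scale, the item 2 cut is the benchmark at or just below that scale's 95th percentile. It therefore flags at least as many notes as the percentile, and the same notes only if no rating lies between the two cuts. With two scales and one pooled cut, this would have to hold on both scales at once. The pooled cut can also lie below the child benchmark, which reverses the disagreement for children.

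**Hand example** (assumed ratings, 400 adults and 100 children):

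- Adults: 24 at or above 9 weeks (6%), 17 at or above 12 weeks, 8 at or above 26 weeks (2%).
- Children: 8 at or above 11 weeks and the same 8 at or above 12 weeks, 6 at or above 22 months (6%), fewer than 5 at or above 7.5 years.
- Section 3.3: 17 + 8 = 25, and 25/500 = 5.0%, so the cut is about 12 weeks and 25 notes are flagged.
- Item 2, 5% within each scale: cuts of 9 weeks and 22 months, flagging 24 + 6 = 30. Notes classified differently: (24 − 17) + (8 − 6) = 9.
- Item 2, 5% over all patients, same benchmark rank on both scales: 9 and 11 weeks give 24 + 8 = 32 (6.4%). The next rank gives 8 + 6 = 14 (2.8%), which is too few. So 32 are flagged and 32 − 25 = 7 differ.

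Under the within-scale count, an adult note rated 10 weeks is severe only by item 2. A child note rated 4 months, which lies on the 0.5-month slider grid, is severe only by Section 3.3.

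**Simulation.** All distributional inputs are assumptions:

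- Zero-inflated lognormal harm in days, with 40, 60 or 80% zeros.
- Median non-zero rating of 1 or 5 days; log SD of 2.0 or 2.5.
- Children 20 or 40% of patients, with ratings 1.3 times the adult level.
- Ratings moved to the Table 1 slider grid and capped at the top benchmark.

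This makes 24 settings. The 500 patients are the approximate target in Section 2.1. The 300 is an assumption, because Section 5.4 states "we are throwing out all observations from prior to 2/25 in any analyses that use MO generated outcomes" without giving the number left. Entries are the range across settings of the median count per setting.

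| | N = 500 | N = 300 |
|---|---|---|
| Section 3.3: unassisted notes flagged | 25–26 | 15 |
| Item 2, 5% within scale: flagged | 35–107 | 22–63 |
| Item 2, 5% over all patients: flagged | 31–104 | 20–58 |
| Classified differently, within scale | 10–81 | 7–47 |
| Classified differently, all patients | 7–78 | 5–43 |

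The mid-range results at N = 500 are 52 flagged and 27 classified differently (within scale), or 40 flagged and about 18 classified differently (all patients).

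A separate calculation used other assumptions: 30, 50 or 70% zeros, ratings uniform within bins, and the 5% counted within each scale. It gave a narrower gap: 6.8 to 8.2% flagged by item 2 (34 to 41 of 500) against 5.0% by Section 3.3, with 2.0 to 3.4% of notes (10 to 17) classified differently.

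**The case against.** The strongest reply is that precedence is nearly given. Item 2 is a summary line, the SAP says the construction follows, and Section 3.3 supplies an explicit definition. That does favour Section 3.3, and it is why keeping Section 3.3 is the simplest remedy. It does not remove the conflict. A detailed description should preserve what it details, whereas Section 3.3 drops the benchmark and replaces the appropriate scale with pooling.

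A second reply reads the percentile as one of scale position, the interval chosen, rather than of the rating. On that reading Section 3.3 almost coincides with the benchmark rule counted over all patients. But Section 3.3 speaks of a harm rating, and Section 2.3.1 obtains that rating from the slider within the interval, so the reading fits poorly.

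A third reply concerns the numbers, and part of it stands. Without heaping, the two rules flag identical notes in only a small share of runs (up to 6.5% in any setting at N = 500). That depends on raters not favouring the benchmarks. If half of the non-zero ratings move to the nearest benchmark, the highest share of identical runs in any setting rises to about 24% (within scale) or 52% (all patients). With full heaping it is about 78% or 98%. The low agreement should not be relied on, and the counts are illustrations. They also cover unassisted notes only and say nothing about the size or precision of the treatment effect.

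It is also fair that Section 3.3 does not state the percentile's denominator. Its remark about many zeros implies all unassisted notes with no-error notes as zero, but explicit zero-coding appears only in Section 3.4, for outcome 3.

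**Conclusion.** The concern holds. Section 3 item 2 and Section 3.3 define the same primary outcome by different rules, and nothing in the SAP reconciles them. This rests on the text alone. The practical size depends on an unknown rating distribution. Across the assumed distributions at 500 patients, the benchmark rule flags from 31 to 107 unassisted notes where the percentile rule flags about 25. With so few events, reclassifying even 7 to 10 notes matters. The percentile share of about 5% assumes that all unassisted notes enter the denominator, that no-error notes count as zero, and that ties are few. As this is one of four primary outcomes, the wording must be settled before any analysis by treatment status.

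**What to change.** Keep one definition and state it identically in Section 3 item 2 and Section 3.3. Delete the other or label it a sensitivity analysis. The simplest course is to make Section 3.3 primary, with item 2 reworded along these lines: *An indicator for an error in the treatment plan with a harm rating at or above the 95th percentile of ratings over all unassisted notes, counting notes without error as zero and pooling the child and adult scales (Section 3.3).*

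Whichever rule is kept:

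- State whether the cut is scale-specific or pooled.
- If the benchmark rule survives in any role, state whether the 5% is counted within each scale or over all patients.
- Report the realised unassisted share.

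The cost is SAP wording, with no new data. Each choice has a drawback: the percentile rule gives fewer events, and the benchmark rule leaves the event share unknown until the ratings are in.

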3.4 An indicator for the better treatment plan

Based on the DALY rating of SOAP Note A vs. B (counting instances with no errors as 0 DALY loss) we will define an indicator that is 1 if the SOAP Note has the better treatment plan (lower DALY loss). This indicator is 0 for both notes if the notes are judged to be the same according to this question, asked after the MO rated Note A:

Are there any *meaningful* differences in the treatment plans of SOAP Note A and B?

Only if the answer is “yes” or “unsure”, the review of SOAP Note B proceeds.

3.5 Treatment Misallocation Based on Objective Conditions

All at-risk patients in our study will receive malaria, anemia and UTI screening. We define eligibility for testing in Appendix A and the treatment guidelines for each condition in Appendix B.

We will construct a dataset with one observation for each (patient, screening test, note), up to six per patient. We exclude (patient, test) data pairs where the test was not conducted due to our demographic criteria (only women/girls 7 years of age or older are tested for UTI, only adults are tested for anemia). We include (patient,test) combinations where our symptom screen determines the patient is eligible but does not need to be tested and label them as zeros.

We construct an indicator of treatment misallocation that records whether a patient was incorrectly treated for a condition based on the test result or lack of symptoms. The variable is coded as 1 if the patient tested positive and either received inappropriate or no treatment according to the guidelines above. It is also coded as 1 if the patient tested negative or was not tested based on the symptom screen but received treatment for the condition. The variable is only coded as zero if the patient tested negative and was correctly not treated for the corresponding condition, or if they tested positive and received the correct treatment.

Note that some treatments can be given for other conditions or without a screening test, such as antibiotics or iron supplements. In cases where the test was negative but a relevant treatment was received, an MD will conduct a blinded review and code the observation as either a match or mismatch. We will use the “clinical indication,” a diagnosis code that is recorded for each individual prescription drug, as auxiliary data for this exercise.

In cases where the provider created a treatment plan that conditions on the result of medical testing we will interpret this plan based on the actual test results. For example, if the CHEW recommends a malaria test and the plan contains the correct malaria treatment conditional on a positive test result and no malaria treatment when the test is negative, the indicator will equal 0 for both a positive and a negative test result.

4 Secondary Outcomes

Our study will also estimate effects on a range of secondary outcomes. Unless otherwise indicated we will use the same analysis approach as above.

4.1 Alignment of Diagnosis and Treatment Between CHEWs and MOs

Separately from the MO’s subjective evaluation of the CHEW notes, we will assess to what degree the CHEW’s and MO’s conditional notes agree with each other.

For each medication in the CHEW’s treatment plan, there is a “clinical indication” (the diagnosis associated with the drug) along with an indicator that specifies if a given prescription is conditional on a medical test result. We will assess three indicators of a match:

- any match of the contents of the “clinical indication” field across medications;
- any match of the contents of the “medication” field across indications, including whether the medication is conditional on a test or not;
- a match of both medication and indication (and test conditionality).

Since CHEWs often use less specific diagnosis categories, and medications can be given as different formulations or prescribed with a brand name vs. a generic names but with the same medical properties, we will sort the diagnoses of MOs and CHEWs by ICD10 code, along with the associated treatment choices (but without indicating the SOAP note type that contained the information) and ask an MD to create families of diagnoses and associated groups of medications that are appropriate for the family of diagnoses and provide the same or similar treatment. Note that the same treatment may be associated with multiple diagnosis families (e.g. a broad spectrum antibiotic). For the first two items above, we will code as a match if the diagnoses (treatments) appear in the same family of diagnoses (treatments). For the last item, we will code as a match only if the diagnoses appear in the same family and the treatments appear in the same associated treatment family.

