2.2 Patient EMR data

All patient data is saved in the EMR. At various points, this data is collated into SOAP notes (structured text files describing subjective and objective signs and symptoms, the provider's assessment (diagnosis), and the treatment plan).

The SOAP notes that are saved are:

- “Unassisted” SOAP note created on initial patient consultation and submitted to LLM: contains care plan conditional on results of requested medical tests, randomly labeled SOAP A or B
- “Assisted” SOAP note created after LLM feedback was received: conditional care plan, randomly labeled B or A
- Conditional MO SOAP note: conditional care plan, created by MO prior to receiving laboratory test results
- Patient discharge SOAP note: patient care plan created by MO after receiving laboratory test results and communicated to patient
- Final MO SOAP note: patient care plan created after reviewing study medical tests (malaria, anemia, UTI).

In addition, we have the values of individual EMR fields that make up these SOAP notes, e.g. test results, diagnoses, prescriptions, etc., including patient demographics and vital signs.

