4.4 Medical Testing Decisions

We will assess the potential misallocation of medical testing in two ways. First, we will measure it based on the screening test outcome. For each test type, we will create an indicator that is coded as 1 if the CHEW recommends conducting a test that turns out to be negative, and a second indicator that is 1 if the CHEW neglects to request a test that turns out to be positive.

Second, we will also construct a (patient,test,note) level indicator that measures whether the CHEW and MO requested the same or a comparable medical test (e.g. the CHEW requested a malaria RDT whereas the MO requested a malaria bloodsmear).

Finally, we will combine these indicators and count as a mismatch if and only if either: i) a test was not requested by the CHEW but was positive, or ii) the test was requested by the cCHEW but the result was negative and no equivalent test was ordered by the MO. This accounts for the possibility that good clinicians might sometimes order tests which are more likely to be negative “just in case”.

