Children: Ferrous Sulfate 125mg/ml syrup 3-6mg/kg/day for one month

Pregnant women: Ferrous Sulfate 200 mg by mouth twice or thrice daily for one month

Severe anemia: Refer for transfusion

- For UTI (uncomplicated), conditional on testing positive (and meeting the symptom screen), the essential treatment guidelines are:

Adults: first-line treatment Nitrofurantoin 100 mg by mouth twice daily for 7 days

OR

second-line treatment Cotrimoxazole 960 mg by mouth twice daily for 5 days

Children: Cotrimoxazole 8-10 mg/Kg/day by mouth divided twice daily for 5 days

Pregnant women in third trimester only:

Amoxicillin 500 mg by mouth every 8 hours for 7 days

OR

Amoxicillin/Clavulanate 500/125 mg by mouth twice daily for 3-7 days

OR

Cephalexin 500 mg by mouth twice daily for 7 days

C Benchmarks for Healthy Time Lost

The DALY scale has 9 benchmarks from 0 minutes to 23 years (28 years for children), generating 8 “bins” each. In detail, the benchmarks are shown in Table 1.

Adult scale

Summary description	Detailed description	Lower interval endpoint	Upper interval startpoint	Gridpoints
No harm for the patient.	No harm for the patient	0 minutes	0	1 min
Minimal side effects for a few days from unnecessary medication.	Harm: Minimal symptoms for a few days Error: Unnecessary medication given Ex.: Antimalarial prescription for a viral URI.	20 mins	20 mins	5 mins (hrs/mins)
Mild side effects for a few days from unnecessary medication.	Harm: Mild symptoms for a few days Error: Unnecessary medication given Ex.: Antibiotic prescription for a viral URI	150 mins	2hrs 30 mins	30 mins (hrs/mins)
Mild side effects for weeks to months from incorrect medication dosing.	Harm: Mild symptoms for weeks to months Error: Unnecessarily high dose of medication for a year Ex.: High-dose amiodarone (for high blood pressure), risking leg swelling.	24 hrs	1 day	.5 days (day)
Occasional symptom flares for a year from delaying treatment for a chronic condition.	Harm: Occasional symptom flares for a year Error: Treatment for chronic condition delayed by a year Ex.: Not lowering urate in patient with gout flares.	8 days	1 wk 1d	1 day (wk, day)
Slight increase in risk of death from not giving treatment for an acute uncomplicated infection.	Harm: Slight increase in risk of death Error: Effective treatment for acute uncomplicated infection not given Ex.: Failing to treat uncomplicated malaria.	9 wk	2 mo	1 wk (mo,wk)

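### Section 4.1 credits only shared prescription entries, so agreeing on no drug, or stopping a drug the MO does not give, adds nothing to measured CHEW–MO agreement

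*SAP*

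**What the plan says.** The aim in section 4.1 is stated plainly: "we will assess to what degree the CHEW’s and MO’s conditional notes agree with each other". The raw material is prescription-linked: "For each medication in the CHEW’s treatment plan, there is a “clinical indication” (the diagnosis associated with the drug"), together with a flag for whether the prescription depends on a test. Section 3.5 likewise describes the indication as recorded for each individual drug.

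Three indicators follow:

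- indication: "any match of the contents of the “clinical indication” field across medications";
- medication: "any match of the contents of the “medication” field across indications, including whether the medication is conditional on a test or not";
- combined: "a match of both medication and indication (and test conditionality").

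An MD groups diagnoses and drugs into families. The first two indicators are matches if the entries share a family. The combined one is a match only if both diagnosis and treatment do. Nothing is said about notes that contain no drug.

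Section 2.2 says the study also holds the "values of individual EMR fields that make up these SOAP notes, e.g. test results, diagnoses, prescriptions, etc", so a diagnosis is available whether or not a drug is attached to it. In section 4.4, the second testing indicator "measures whether the CHEW and MO requested the same or a comparable medical test"; the case where neither requested it is not mentioned. By the opening of section 4, secondary outcomes use the patient fixed-effect regression of section 3.1 unless otherwise indicated.

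**The concern.** Agreement has two sides: giving what the MO gives, and not giving what the MO does not give. The 4.1 indicators see only the first. A patient whom both providers would send home without a drug has no field to match and is recorded no differently from one given a drug the MO would not use. A diagnosis without a drug does not enter at all.

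This matters because LLM feedback may change how much is prescribed. Unnecessary medication is the error behind the two lowest non-zero benchmarks on both scales in Appendix C, Table 1; one example there is "Antibiotic prescription for a viral URI". If assistance led CHEWs to drop such drugs in line with the MO, 4.1 would not show it. If assistance led them to add drugs, 4.1 could rise through a chance match and would never fall because of the extras.

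**Working it through.** The SAP gives no figure tied to this outcome, so there is nothing to reproduce. The check applies the rules to cases.

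**1. Patients to whom the MO gives no drug.** The MO's note has no medication or indication entry.

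- If the absence of a match is coded 0, all three indicators are 0 for both the unassisted and the assisted note. The within-patient difference is 0 whatever the CHEW does.
- If both-empty pairs are set to missing, a CHEW note that moves from one drug to none goes from 0 to missing. A single remaining note contributes nothing to the assistance coefficient under patient fixed effects.

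Either way the patient cannot show a gain. For the combined indicator the zero follows from the stated only-if rule. For the other two it is the literal reading.

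**2. Stopping or adding one drug the MO does not give.** Take three possible drugs and let each note hold any subset. Choose the unshared drug (3 ways). Each of the other two drugs may be in neither note, either one, or both (4 states each). That gives 3 × 4 × 4 = 48 possible changes in each direction.

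| Scoring rule | Stopping raises the score |
|---|---|
| Any match, as written | 0 of 48 |
| Any match, both-empty coded 1 | 3 of 48 |
| Shared/union, both-empty coded 1 | 24 of 48 |

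Under the rule as written, adding such a drug lowers the score in 0 of 48. The 3 are the cases where the other two drugs are absent from both notes (3 × 1 × 1). The 24 are those cases plus the ones where at least one other drug is shared: 3 × [1 + (16 − 9)] = 24. In the remaining 24 no drug is shared, and overlap stays at 0. These are counts of possible changes, not frequencies expected in the data.

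**3. Size.** Let s be the share of patients to whom the MO gives no drug, g the rise with assistance in the CHEW's no-drug rate among them, and e the effect on the medication match in everyone else. With zero coding the recorded effect is (1 − s)e. With both-empty coded as a match it is (1 − s)e + sg. The difference is sg, and the recorded agreement level cannot exceed 1 − s. The SAP gives neither s nor g. Assuming g = 0.20 purely for illustration:

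- s = 0.05: 0.05 × 0.20 = 1 percentage point
- s = 0.10: 2 points
- s = 0.30: 6 points
- s = 0.40: 8 points

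If g were negative, the rule would hide a loss in the same way.

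**4. Testing, section 4.4.** Two of the testing measures already handle overuse. For a negative test that the MO did not order, a CHEW who drops the request moves the negative-test indicator from 1 to 0 and the combined mismatch from 1 to 0. Joint non-request with a negative result is not a combined mismatch. Only the shared-request indicator is open: read literally it is 0 when neither requests; read as concordance it is 1.

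**The case against.** The strongest reply is that the SAP never says joint absence is disagreement. That is right for the indication and medication indicators, where a reader might infer an explicit zero that is not written. It does not hold for the combined indicator, whose only-if rule leaves no room for a match without a drug. Nor does missing coding rescue the first two, as step 1 shows.

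A reader might also infer that dropping an unneeded test earns nothing in section 4.4. The document does not support that: the negative-test and combined indicators both credit it, and the remaining indicator is ambiguous rather than wrong.

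A third tempting inference is that the trial would miss reduced overuse altogether. It would not. The any-error outcome (3.2), the better-plan outcome (3.4), misallocation (3.5), overprescription (4.2) and the MO's ratings of unnecessary elements (2.3.1, reported under 4.5) all register some of it. Part of the objection therefore stands. But 3.5 and 4.2 cover only malaria, anemia and UTI. The others rest on the MO's judgement, for which section 5.1 itself plans unblinding checks. Section 4.1 is offered as separate from that judgement and covers all conditions.

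Finally, coding both-empty as 1 is not a full remedy, since it reaches only 3 of the 48 changes. It would also be wrong to record a combined match when neither note has a drug but the diagnoses differ. Both points are accepted in the fix.

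**Conclusion.** The concern holds for section 4.1. Following the stated rules, patients to whom the MO gives no drug contribute no gain to any of the three indicators. Among the rest, the any-match rule is blind to unshared drugs. If assistance brings CHEWs closer to the MO by removing drugs, the agreement effect is attenuated; it is not reversed.

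The size cannot be computed from the SAP. The 1 to 8 points above rest wholly on assumed values of s and g and should not be quoted as an estimate. The outcome is secondary and the primary outcomes are unaffected, so this is a change worth making rather than a threat to the main conclusions. For section 4.4 the conclusion is limited to one unclear definition.

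**What to change.** In section 4.1:

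- Take the diagnosis match from the EMR diagnosis values described in section 2.2, so that diagnoses without a drug count.
- For the medication match, code both-empty as 1 and only-one-empty as 0.
- For the combined match, code both-empty as 1 only if the EMR diagnoses also match.
- Report the share of pairs that are both-empty, separately for assisted and unassisted notes.
- Add a set-overlap version (shared drugs divided by all drugs in either note, with both-empty set to 1), so that unshared drugs count.

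In section 4.4, state that the second indicator equals 1 when both or neither requested the same or a comparable test, and 0 otherwise. Leave the negative-test and combined indicators as they are.

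The cost is a few sentences and a small coding change, with no new patient data; the MD's diagnosis families must also cover diagnoses that carry no drug. The downside is that agreement levels rise because joint absence now counts, which is why the both-empty share should be shown beside them. The coding should be fixed before this outcome is analysed by assistance status.
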